6. TRIAL PARTICIPANT DISPOSITION

6.1 Disposition of Participants

Final disposition for all study participants will be summarized using the following CONSORT flow chart.

6.2 Protocol Deviations

Protocol deviations related to study inclusion or exclusion criteria, the conduct of the study, and inappropriate enrollment will be summarized by site, and overall, in the form of tables and listings. The following protocol deviations will be summarized:

- Inappropriate enrollment
- Failure to follow randomization or blinding procedures
- Conduct of non-protocol procedure
- Improper SAE
- Unreported SAE
- Breach of confidentiality
- Physical assessment deviation
- Lab assessment deviation
- Staff performing duties that they are not qualified to perform
- Use of non-IRB/EC-approved materials
- Informed consent process deviation
- Other

7. BASELINE DATA

Participants' baseline characteristics will be presented by site, HIV status, study arm, and overall.

- Demographics, including age, race, ethnicity, self-identified gender and sexual orientation.
- Drug use and overdose history including: the types of drugs taken (stimulants, opioids, other); ways the drugs were taken; and the number of days drugs were taken in the past month. Overdose history will be summarized by the type of drug leading to overdose on and the number of times overdosed.
- Delivery of the intervention will be described by summarizing the number of navigation sessions per participant, the location and length of the sessions, and the topics addressed.

8. EFFICACY/EFFECTIVENESS ANALYSES

Primary Outcomes:

Among the enrolled HIV-negative cohort:

- Documented current use of MOUD defined as: alive, retained, with biological evidence of MOUD (defined in section 5) and a current MOUD prescription or proof of current receipt of MOUD from a clinic that does not provide individual MOUD prescriptions (e.g., methadone clinics) at the week 26 visit
- Current use of PrEP defined as: alive, retained, HIV-negative, with detectable PrEP (defined in section 5) at the week 26 visit

For the primary outcome of MOUD use, a Generalized Linear Model (GLM) for binary outcomes using the identity link will be performed with treatment arm and site as covariates. The proportions of participants who meet the MOUD endpoint criteria (by-arm, and by-site-by-arm) at week 26 will be provided along with the estimate and 95% confidence interval for the difference in proportions.

For the primary outcome of PrEP use, a Generalized Linear Model (GLM) for binary outcomes using the identity link will be performed with treatment arm and site as covariates. The proportions of participants who meet the PrEP endpoint criteria (by-arm, and by-site-by-arm) at week 26 will be provided along with the estimate and 95% confidence interval for the difference in proportions.

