2.5 Sample Size and Power

Sample sizes are chosen to provide sufficient power for both the HIV-related and MOUD-related primary outcomes. By computing sample sizes based on each individual outcome separately and choosing the largest sample size needed for either outcome, high power is achieved for both individual outcomes. Prior work in PWID populations suggests that uptake of MOUD, ART, and PrEP in the control condition will likely be modest;^{1,2} we anticipate 25% uptake of MOUD, 42.5% achieving viral suppression, and 5% uptake of PrEP in the control arm.

Sample sizes are computed to provide 90% power to detect a fifteen-percentage point difference in the proportion of participants achieving success, assuming a 5% type-I error rate (two-sided). A sample of 400 participants is needed to detect a 15-point difference in MOUD use (25% vs. 40%) between the active control and intervention arm at 26 weeks. Approximately 216 people without HIV would be needed to see a 15-point difference in PrEP uptake (5% vs. 20%). To cover both HIV and MOUD outcomes, 400 people without HIV will be needed. Approximately 10% of the study population is expected to be living with HIV – insufficient to accommodate a fully powered subgroup - but because this subgroup is expected to have very different rates of HIV-related success than the people without HIV subgroup, it will be important to analyze these participants separately. To assure 400 people without HIV, the target sample size will be augmented by 50 for a combined total of 450 participants, where 40-50 of those are expected to be people living with HIV.

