These outcomes will be modeled and summarized using the same strategy as specified for the primary outcome in section 8 above.

- d) Decreases opioid and polysubstance use at 26 and 52 weeks

Outcome:

- Opioids (natural or synthetic) detected in urine samples for those retained at the week 26 and 52 visits (visits analyzed separately).
- Opioids (natural or synthetic) detected, along with stimulants (methamphetamine, cocaine), xylazine and/or benzodiazepines detected in urine samples at the week 26 and 52 visits (visits analyzed separately).

This objective will be analyzed only in those giving a urine sample at the respective visit (week 26 or week 52).

Opioids (natural or synthetic) include opiates, fentanyl and synthetic opioids.

Opiate detection includes 6-mam, codeine, dihydrocodeine, heroin, hydrocodone, hydromorphone, morphine, morphine glucuronide naloxone, and normorphine.

Fentanyl detection includes 4-ANPP, acetyl fentanyl, alfentanil, fentanyl, FIBF, furanyl fentanyl, methoxyacetyl fentanyl, norfentanyl, para-chlorofentanyl, para-fluorofentanyl, and valeryl fentanyl.

Synthetic Opioid detection includes isotonitazene, meperidine, metonitazene, noroxycodone, oxycodone, oxymorphone, tapentadol, tramadol, and U-47700.

Stimulant detection includes amphetamine, MDA, MDEA, MDMA, methamphetamine, methylphenidate, phentermine, benzoyllecgonine, cocaethylene, and cocaine.

Benzodiazepine detection includes alpha-hydroxyalprazolam, alprazolam, carisoprodol, chlordiazepoxide, clonazepam, diazepam, flurazepam, lorazepam, nordiazepam, oxazepam, and temazepam.

These outcomes will be modeled and summarized using the same strategy as specified for the primary outcome in section 8 above.

e) Decreases prevalence of bacterial STIs at 26 and 52 weeks

Outcome:

- Gonorrhea, chlamydia, or new or prevalent syphilis infection detected via local labs for those retained at the week 26 and 52 visits (visits analyzed separately).

This objective will be analyzed only in those giving a specimen and having a valid test result at the respective visit (week 26 or week 52).

Negative for syphilis, at any visit, is defined as a negative/not-detected non-treponemal test; or a positive non-treponemal test and a negative/not-detected treponemal test (this would be considered a false-positive test and thus considered negative for the visit).

Prevalent syphilis is defined as a positive non-treponemal test and a positive treponemal test, with a titer value $\geq 1:8$.

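### The identity-link binomial model for the primary PrEP outcome is poorly suited to a 5% control rate: with no true effect, its Wald interval would exclude zero in about 14–15% of trials, not 5%

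*SAP*

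**What the plan says.** SAP Section 8 sets the primary PrEP analysis: "For the primary outcome of PrEP use, a Generalized Linear Model (GLM) for binary outcomes using the identity link will be performed". Its only model terms are arm and site. The result to be reported is "the estimate and 95% confidence interval for the difference in proportions", beside the raw proportions for each arm and for each arm within site. Neither Section 8 nor the general methods in Section 5 names a distribution, a variance estimator, an arm-by-site term or a rule for a fit that does not converge or lies on the boundary.

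Section 2.5 gives the planning figures: "Sample sizes are computed to provide 90% power to detect a fifteen-percentage point difference". The error rate behind that calculation is a two-sided 5%. For PrEP it says "Approximately 216 people without HIV would be needed to see a 15-point difference in PrEP uptake (5% vs. 20", the second rate also being a percentage. Because MOUD needs more participants, "400 people without HIV will be needed". Section 2.3 expects about 80 HIV-negative participants at each of five sites, randomized 1:1 within site and HIV status.

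Section 10 applies the same model to many secondary outcomes: "These outcomes will be modeled and summarized using the same strategy as specified for the primary outcome in section 8 above".

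**The concern.** A binomial model with identity link requires every fitted probability to stay between 0 and 1, and with only arm and site terms it imposes one risk difference on all sites. With about 2 expected successes per control site (40 × 0.05), a site with none is likely, and the best fit then tends to sit at a fitted probability of zero. Ordinary Wald theory does not apply there.

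The fit also weights each site-arm cell by n/(p(1−p)). For n = 40 this is 250 at p = 0.20, 842 at p = 0.05 and 4,040 at p = 0.01, and it grows without limit as p nears zero. Cells that happen to have few successes are therefore treated as very precise. This can make the interval too short. If the risk difference is smaller where rates are low, it also pulls the estimate toward those sites.

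At stake are the error rate of a primary endpoint and an unplanned choice of method, made with arm-level results in view, if the fit misbehaves.

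**Working it through.** **Planning figures.** The SAP's sample sizes reproduce. For MOUD, the unpooled normal formula gives (1.960 + 1.282)² × (0.25×0.75 + 0.40×0.60)/0.15² = 10.507 × 19 = 199.6 per arm, or 399.3 in total, rounded up to 400. For PrEP, a two-sided Fisher exact test has 90.2% power at 212 and 90.9% at 216. Normal approximations give 194 (unpooled), 202 (pooled) and 228 (continuity-corrected). The sample size is not in dispute.

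**Inputs for the check.** Five sites; 80/2 = 40 per arm per site (Section 2.3); 5% vs 20% (Section 2.5). A missed week 26 visit counts as negative (Section 3.2), so denominators stay near 40.

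**Zero cells.** P(0 of 40 at one control site) = 0.95^40 = 0.1285. P(at least one of five) = 1 − (1 − 0.1285)^5 = 1 − 0.503 = 49.7%.

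**Simulation.** Binomial maximum likelihood for site + arm, with probabilities constrained to 0–1 and Wald intervals from the Fisher information at the estimate. Ranges reflect separate runs of 1,000 to 8,000 trials. Differences are in percentage points. Scenarios in which sites differ are assumptions, because the SAP gives no between-site variation.

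| Scenario | Boundary fits | True difference | Mean estimate | Wald coverage |
|---|---|---|---|---|
| 5% vs 20% at every site | 45–48% | 15 | 15.0–15.1 | 93–94% |
| 5% in both arms | not tabulated | 0 | not tabulated | 85–86% |
| Control 3–7%, common 15-point effect | 55% | 15 | 15.0 | 93.5% |
| Control 1–9%, common 15-point effect | 81% | 15 | 15.0 | 93.9% |
| Control 5%, treated 10–30% | 44% | 15 | 14.2 | 91.0% |
| Control 3–7%, treated four times that | 55% | 15 | 14.1–14.4 | 89–92% |
| Control 1–9%, treated four times that | 80% | 15 | about 12 | 76–77% |

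**Type I error.** Coverage of 85.8% with no effect means that 100 − 85.8 = 14.2% of intervals exclude zero. One run split this as 6.7% in one direction and 7.0% in the other. Profile-likelihood intervals help only in part (about 90%). At 5% vs 10% everywhere, Wald coverage was 90.5%.

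**Direction of the bias.** In the last row, p(1−p) summed over the two arms is 0.0099 + 0.0384 = 0.0483 at the 1%/4% site and 0.0819 + 0.2304 = 0.3123 at the 9%/36% site. At those true rates, inverse-variance weighting gives the first site 0.3123/0.0483 = 6.5 times the weight of the second, although its difference is 3 points rather than 27. The model uses fitted rather than true rates, so this shows the direction and not the exact size.

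**Alternative on the same design.** The average of within-site differences, or a linear model with robust standard errors, averaged 14.9–15.0 where the truth was 15, with 94.4–95.0% coverage, including where site effects differed. Coverage was about 95% with 5% in both arms. At 5% vs 20% everywhere, the empirical standard deviation was 3.20 points for the average of site differences and 3.26 for the binomial fit, so no precision is lost.

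**The case against.** At the planned rates the model does its job. With 5% vs 20% everywhere there is no bias, coverage is about 93–94%, and the null was rejected in 99.9% of trials, against 99.7% for the stratified difference. This stands.

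A reader might take 48% as the chance that the analysis fails. The documents do not support that. The constrained maximum-likelihood estimate still exists on the boundary. One standard iterative fit failed in 3.1% of trials and returned a negative fitted probability in 15%. Other software may behave differently, and the SAP names none.

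A reader might also infer that any difference between sites biases the result. It does not: with a common 15-point effect and control rates from 1% to 9%, the mean was 15.0 and coverage 93.9%, despite 81% boundary fits. Bias needs a risk difference that varies by site, and its size rests on assumed variation.

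Binomial is also an inference from the wording. An identity-link fit with robust variance arguably fits the text and avoids the problem. Finally, Section 8 requires proportions for each arm within site, and Section 5 requires deviations to be described, so a zero cell would be visible. These are safeguards of disclosure; they do not say what to do.

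None of this answers the no-effect case, which needs no variation between sites.

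**Conclusion.** The point holds for the PrEP outcome, on the reading that the model is binomial with model-based Wald intervals. On the SAP's own control rate and site sizes, boundary fits occur in about 45–48% of trials without a stated fallback. With no effect, the two-sided type I error is about 14–15% against the 5% in Section 2.5. That rests on 5% use in both arms, the no-effect counterpart of the planned control rate.

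The bias is conditional. If the risk difference varies by site, the estimate falls short of 15 points by roughly 0.6 to 0.9 in the milder fourfold scenario and by about 3 in the wide one. The SAP gives no basis for choosing between these or for expecting either.

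It would be tempting to extend the point to MOUD because the model is the same. At 25% vs 40% there were no boundary fits, so the MOUD model need not change on this ground.

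**What to change.** In Section 8, name as the analysis of record for PrEP either a site-stratified risk difference (Mantel-Haenszel or the average of within-site differences) with its 95% confidence interval, or an identity-link linear model with arm and site and robust variance. State the variance estimator explicitly.

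In Section 10, apply the same choice to the inherited secondary outcomes with low event rates. Protective PrEP levels are the clearest case, since they can be no more frequent than detectable PrEP.

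The cost is a few lines of SAP text and code, settled before arm-level results are analysed. The difference in proportions remains the effect measure and the sample size is unaffected.

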9. SAFETY ANALYSES

In this study, the only drugs that will be dispensed or prescribed will be US FDA-approved medications for treatment or prevention of OUD, HIV, and STIs and prescriptions for contraceptives, primary care concerns, and chronic conditions, if indicated. There are no investigational products in this protocol. Therefore, there will be no monitoring or reporting of unanticipated treatment-related risks with the following exception: site investigators will report to the FDA any serious adverse events that are “unexpected” per the current version of the package insert for drugs provided for MOUD, ART or PrEP via the FDA’s MedWatch form, copying the RSC Safety Office.

9.1 Adverse Events and Deaths

Adverse events (AEs) that study staff become aware of will be recorded in source documentation and will be assessed for seriousness. Non-serious AEs will not be reported in the study database and referrals for care will be provided as necessary. Only Serious adverse events (SAEs) will be reported in form of tables and listings categorized by system organ class, severity grade (The Division of AIDS Table for Grading the Severity of Adult and Pediatric Adverse Events, Corrected Version 2.1, July 2017. <https://rsc.niaid.nih.gov/clinical-research-sites/daids-adverse-event-grading-tables>), HIV status and arm. Serious adverse events (SAEs) are those AEs that result in one or more of the following outcomes:

- Death
- A life-threatening (i.e., an immediate threat to life) event
- Requires in-patient hospitalization or prolongation of an existing hospitalization
- A persistent or significant incapacity or substantial disruption of the ability to conduct normal life functions
- A congenital anomaly/birth defect
- A medically important event that may not be immediately life-threatening or result in death or hospitalization but may jeopardize the patient or may require intervention to prevent one of the other outcomes listed in the definition above

Examples of SAEs that can be expected to occur during this study include deaths (e.g., overdoses or other addiction-related deaths) and life-threatening events requiring intervention (e.g., overdose reversals).

9.2 Other Safety Measures

Pregnancy will be presented in the form of listings by site, study arm and HIV-status.

10. SECONDARY ENDPOINTS

1. **To evaluate whether “one stop” integrated health services delivered in a mobile unit, supported by peer navigation, compared to peer navigation to similar health services available at community-based agencies, the following endpoint(s) will be assessed:**
 - a) Improves use of MOUD at 52 weeks compared to the active control condition

Outcomes:

- Documented current use of MOUD: alive, retained, with biological evidence of MOUD (as defined above) at the week 52 visit and a MOUD prescription current at 52 weeks after enrollment or proof of current receipt of MOUD from a clinic that does not provide individual MOUD prescriptions (e.g., methadone clinics) at the week 52 visit
- Documented use of MOUD during the study: a MOUD prescription documented during the 52 weeks of study follow-up or proof of current receipt of MOUD from a clinic that does not provide individual MOUD prescriptions (e.g., methadone clinics) during the 52 weeks of study follow-up

These outcomes will be modeled and summarized using the same strategy as specified for the primary outcome in section 8 above.

- b) Increases rates of viral suppression among people enrolled living with HIV, at 26 and 52 weeks

Outcome:

- Among participants living with HIV at enrollment: alive, retained, and virally suppressed (VL <200 copies/mL) at the week 26 and 52 visits, separately.

The proportion of participants achieving the viral suppression outcome will be computed and presented by arm and within site by arm, along with exact Clopper-Pearson 95% confidence intervals using F-quantiles based on the Binomial distribution. No statistical comparisons between treatment arms will be made.

- c) The intervention increases use of PrEP among people without HIV at 26 and 52 weeks

Outcome:

- Among participants without HIV at enrollment: alive, retained, HIV negative, with detectable PrEP drugs in DBS at the week 52 visit
- Among participants without HIV at enrollment: alive, retained, HIV negative, with protective levels of PrEP drugs in DBS samples at the week 26 and 52 visits

A protective level of oral PrEP³ is defined as:

TFV-DP concentrations ≥ 800 fmol/punch in DBS among those tested for Truvada (TDF-FTC)

TFV-DP concentrations ≥ 950 fmol/punch in DBS among those tested for Descovy (TAF-FTC)

A protective level of long-acting PrEP (Cabotegravir) is defined as plasma concentrations above the four times the PA-IC₉₀ of 166 ng/mL – that is, above 664 ng/mL.

These outcomes will be modeled and summarized using the same strategy as specified for the primary outcome in section 8 above.

- d) Decreases opioid and polysubstance use at 26 and 52 weeks

Outcome:

- Opioids (natural or synthetic) detected in urine samples for those retained at the week 26 and 52 visits (visits analyzed separately).
- Opioids (natural or synthetic) detected, along with stimulants (methamphetamine, cocaine), xylazine and/or benzodiazepines detected in urine samples at the week 26 and 52 visits (visits analyzed separately).

This objective will be analyzed only in those giving a urine sample at the respective visit (week 26 or week 52).

Opioids (natural or synthetic) include opiates, fentanyl and synthetic opioids.

Opiate detection includes 6-mam, codeine, dihydrocodeine, heroin, hydrocodone, hydromorphone, morphine, morphine glucuronide naloxone, and normorphine.

Fentanyl detection includes 4-ANPP, acetyl fentanyl, alfentanil, fentanyl, FIBF, furanyl fentanyl, methoxyacetyl fentanyl, norfentanyl, para-chlorofentanyl, para-fluorofentanyl, and valeryl fentanyl.

Synthetic Opioid detection includes isotonitazene, meperidine, metonitazene, noroxycodone, oxycodone, oxymorphone, tapentadol, tramadol, and U-47700.

Stimulant detection includes amphetamine, MDA, MDEA, MDMA, methamphetamine, methylphenidate, phentermine, benzoyllecgonine, cocaethylene, and cocaine.

Benzodiazepine detection includes alpha-hydroxyalprazolam, alprazolam, carisoprodol, chlordiazepoxide, clonazepam, diazepam, flurazepam, lorazepam, nordiazepam, oxazepam, and temazepam.

These outcomes will be modeled and summarized using the same strategy as specified for the primary outcome in section 8 above.

e) Decreases prevalence of bacterial STIs at 26 and 52 weeks

Outcome:

- Gonorrhea, chlamydia, or new or prevalent syphilis infection detected via local labs for those retained at the week 26 and 52 visits (visits analyzed separately).

This objective will be analyzed only in those giving a specimen and having a valid test result at the respective visit (week 26 or week 52).

Negative for syphilis, at any visit, is defined as a negative/not-detected non-treponemal test; or a positive non-treponemal test and a negative/not-detected treponemal test (this would be considered a false-positive test and thus considered negative for the visit).

Prevalent syphilis is defined as a positive non-treponemal test and a positive treponemal test, with a titer value $\geq 1:8$.

Note: Participants can be non-prevalent (positive tests with tier $< 1:8$) but also not negative for syphilis. Thus, they had syphilis previously, but it is not a prevalent infection.

New syphilis is defined as a positive non-treponemal test and positive treponemal test (regardless of titer value) at a follow-up visit when they were negative at the previous visit.

These outcomes will be modeled and summarized using the same strategy as specified for the primary outcome in section 8 above.

f) Decreases fatal and non-fatal overdose events by 26 and 52 weeks

Outcomes:

- Death, with overdose as cause, collected on or before 26- and on or before 52-week visits, separately.
- Self-report of non-fatal overdose, collected on or before week 26- and on or before 52-week visits, separately.

These outcomes are reported on the SAE log form.

Death, caused by overdose, will be modeled with a time-to-event cox proportional hazards model with treatment arm as a covariate.

Person-time for fatal overdoses will be calculated as follows:

- For those retained (alive) at the visit: time between enrollment and the week 26 or week 52 visit date.
- For those reported deceased by the visit date: time between enrollment and recorded date of death.
- If deceased and no recorded date of death: time between enrollment and the midpoint of last attended visit and termination date.
- Those with no reported death and not retained at week 26 and/or week 52 (or terminated before the visit): use time between enrollment and the last attended visit (or termination date). If no other visit besides enrollment is documented: exclude from the analysis.

Note: Last attended visit can include the enrollment or week 26 visits, an interim visit, or a navigation session

Self-reported non-fatal overdoses will use a Poisson regression model (GLM with log link) with treatment arm as a covariate. We will use the number of reported non-fatal overdoses in the 30 days prior to the respective visit to compare treatment arms.

- g) Increases the proportion of participants with undetectable HCV RNA at 26 and 52 weeks among those with chronic HCV infection at enrollment

Outcome:

- Undetectable HCV RNA at the week 26 and 52 visits (visits analyzed separately) among participants with chronic HCV at enrollment.

The HCV treatment outcome will be modeled and summarized using the same strategy as specified for the primary outcome in section 8 above.

- h) Decreases HCV incidence at 52 weeks, for those who are HCV negative at enrollment

Outcome:

- HCV antibody positive at the week 52 visit among participants who are HCV antibody negative at enrollment.

HCV incidence will be modeled using Poisson regression (GLM with log link), with treatment arm and site as covariates and person years as an offset. Person time will be computed as the number of years from enrollment to the visit date where infection is first detected for participants with incident HCV infection, and from enrollment to the week 52 visit date (or last available visit) for HCV-negative participants with no incident infection.

2. To evaluate whether 26 weeks of “one stop” integrated health services delivered in a mobile health delivery unit, supported by peer navigation, increases MOUD use, viral suppression, and PrEP use at 26 and 52 weeks compared to enrollment, the following endpoint(s) will be assessed:

- In the intervention arm, change over time in the use of MOUD during the study, comparing documented use of MOUD (biological evidence of MOUD - any detectable medications - and a current MOUD prescription or proof of current receipt of MOUD from a clinic that does not provide individual MOUD prescriptions (e.g., methadone clinics)) at 26 and 52 weeks to documented use of MOUD at enrollment. MOUD use is assumed to be zero at enrollment due to study exclusion criteria. Follow-up endpoints will be defined as alive, retained, and having documented MOUD use.
- Among participants living with HIV at enrollment: change over time in the proportion of people with viral suppression (VL<200 copies/mL), comparing 26 and 52 weeks to enrollment. Follow-up endpoints will be defined as alive, retained, and virally suppressed.

- Among participants who were without HIV at enrollment: change over time in the proportion of people with detectable PrEP drugs in DBS at 26 and 52 weeks compared to enrollment. Follow-up endpoints will be defined as alive, retained, and having detectable PrEP.

The viral suppression outcome will not be modelled. We will report the proportions at enrollment, 26 week and 52-week visits, along with exact Clopper-Pearson 95% confidence intervals using F-quantiles based on the Binomial distribution.

Change over time in the MOUD endpoint will be modeled using GEE (one model for 26 weeks compared to enrollment, and another model for 52 weeks compared to enrollment) with a linear link and an exchangeable correlation structure accounting for within-person repeated measures over time. Each model will include an indicator for time point (26 weeks vs enrollment, or 52 weeks vs enrollment) and a covariate for site. The proportion of participants achieving the outcome at each time point will be summarized, along with the estimated difference in proportions and corresponding 95% confidence interval.

Change over time in the PrEP outcome will be modeling and summarized using the same strategy as defined above for MOUD.

3. To evaluate whether 26 weeks of peer navigation to similar health services available at community-based agencies increases MOUD use, viral suppression, and PrEP use at 26 and 52 weeks compared to enrollment, the following endpoint(s) will be assessed:

- In the active control arm, change over time in the use of MOUD during the study, comparing documented use of MOUD (biological evidence of MOUD - any detectable medications - and a current MOUD prescription or proof of current receipt of MOUD from a clinic that does not provide individual MOUD prescriptions (e.g., methadone clinics)) at 26 and 52 weeks to documented MOUD use at enrollment. MOUD use is assumed to be zero at enrollment due to study exclusion criteria. Follow-up endpoints will be defined as alive, retained, and having documented MOUD use.
- In the active control arm among participants living with HIV at enrollment: change over time in the proportion of people with viral suppression (VL<200 copies/mL), comparing 26 and 52 weeks to enrollment. Follow-up endpoints will be defined as alive, retained, and virally suppressed.
- In the active control arm among participants who were without HIV at enrollment: change over time in the proportion of people with detectable PrEP drugs in DBS at 26 and 52 weeks compared to enrollment. Follow-up endpoints will be defined as alive, retained, and having detectable PrEP.

The viral suppression outcome will not be modelled. We will report the proportions at enrollment, 26 week and 52-week visits, along with 95% confidence intervals using exact binomial distribution.

For participants in the control arm, change over time in the MOUD and PrEP outcomes will be modeled and presented using the same strategy as defined in section 2 above for the intervention arm.

4. To document the prevalence of seropositivity for SARS-CoV-2 at baseline, 26 and 52 weeks, the following endpoint(s) will be assessed:

- Laboratory evidence of antibodies to SARS-CoV-2 Overall and by Site (and by arm).

At each of the three timepoints, we will report the proportion of participants with lab evidence of SARS-CoV-2 antibodies (by-arm and by-site-by-arm) at week 26 and week 52. Laboratory evidence of antibodies to SARS-CoV-2

Analyses for Secondary Objectives 5, 6, and 7, along with Process Objectives 1 and 2, will be outlined in a different Analysis Plan document.

